- 10.4 Solicited toxicities to be graded at each evaluation and pretreatment symptoms/conditions to be evaluated based on the schedule of events using the CTCAE v5.0 grading unless otherwise stated in the table below. This regimen has established safety, based on this article [https://www.thelancet.com/journals/lanonc/article/PIIS1470-2045\(22\)00638-6/fulltext](https://www.thelancet.com/journals/lanonc/article/PIIS1470-2045(22)00638-6/fulltext) so the focus is on solicited toxicities and not any adverse event after radiation therapy is completed.

ACUTE TOXICITIES – Upper Proximal Extremity			
CTCAE System/Organ/Class (SOC)	Adverse Event / Symptoms	Baseline	During RT & Preoperative Assessment

General disorders and administration site conditions	Fatigue	X	X
Skin and subcutaneous tissue disorders	Dermatitis Radiation	X	X
	Hyperpigmentation	X	X
Neoplasm benign, malignant and unspecified	Tumor pain	X	X

LATE TOXICITIES – Upper Proximal Extremity		
CTCAE System/Organ/Class (SOC)	Adverse Event / Symptoms	Post-Surgery & Follow Up
Skin and subcutaneous tissue disorders	Hyperpigmentation ¹	X
Vascular	Lymphedema ²	X
General disorders and administration site conditions	Localized edema ¹	X
Musculoskeletal and connective tissue disorders	Fibrosis deep connective tissue ¹	X
	Joint range of motion decreased ²	X
	Osteonecrosis ¹	X

Neoplasm benign, malignant and unspecified	Tumor pain ¹	X
Injury, poisoning and procedural complications	Fracture ¹	X
Gastrointestinal Disorders ¹	Esophageal fistula	X
Respiratory, thoracic and mediastinal disorders	Pneumonitis ¹	X

¹ Specific to radiation / surgery treatment area

² Specific to ipsilateral extremity / region

ACUTE TOXICITIES – Upper Distal Extremity (includes elbow)			
CTCAE System/Organ/Class (SOC)	Adverse Event / Symptoms	Baseline	During RT & Preoperative Assessment
General disorders and administration site conditions	Fatigue	X	X
Skin and subcutaneous tissue disorders	Dermatitis Radiation	X	X
	Hyperpigmentation	X	X
Neoplasm benign, malignant and unspecified	Tumor pain	X	X

LATE TOXICITIES – Upper Distal Extremity (includes elbow)		
CTCAE System/Organ/Class (SOC)	Adverse Event / Symptoms	Post-Surgery & Follow Up
Skin and subcutaneous tissue disorders	Hyperpigmentation ¹	X
Vascular	Lymphedema ²	X
General disorders and administration site conditions	Localized edema ¹	X
Musculoskeletal and connective tissue disorders	Fibrosis deep connective tissue ¹	X
	Joint range of motion decreased ²	X
	Osteonecrosis ¹	X

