Neoplasm benign, malignant and unspecified	Tumor pain ¹	X
Injury, poisoning and procedural complications	Fracture ¹	X

¹ Specific to radiation / surgery treatment area

² Specific to ipsilateral extremity / region

ACUTE TOXICITIES – Lower Proximal Extremity (includes knee)			
CTCAE System/Organ/Class (SOC)	Adverse Event / Symptoms	Baseline	During RT & Preoperative Assessment
General disorders and administration site conditions	Fatigue	X	X

Skin and subcutaneous tissue disorders	Dermatitis Radiation	X	X
	Hyperpigmentation	X	X
Gastrointestinal disorders	Diarrhea	X	X
	Nausea	X	X
	Vomiting	X	X
Renal and urinary disorders	Dysuria	X	X
Neoplasm benign, malignant and unspecified	Tumor pain	X	X

LATE TOXICITIES – Lower Proximal Extremity (includes knee)		
CTCAE System/Organ/Class (SOC)	Adverse Event / Symptoms	Post-Surgery & Follow Up
Skin and subcutaneous tissue disorders	Hyperpigmentation ¹	X
Vascular	Lymphedema ²	X
General disorders and administration site conditions	Localized edema ¹	X
	Fibrosis deep connective tissue ¹	X

Musculoskeletal and connective tissue disorders	Joint range of motion decreased ²	X
	Osteonecrosis ¹	X
Neoplasm benign, malignant and unspecified	Tumor pain ¹	X
Injury, poisoning and procedural complications	Fracture ¹	X
Gastrointestinal Disorders ¹	Anal fistula	X
	Colonic fistula	X
	Duodenal fistula	X
	Ileal fistula	X
	Jejunal fistula	X
	Rectal fistula	X
	Anal ulcer	X
	Colonic ulcer	X
	Duodenal ulcer	X
	Ileal ulcer	X
	Jejunal ulcer	X
	Rectal ulcer	X
	Small intestine ulcer	X
	Anal stenosis	X
	Colonic stenosis	X
	Duodenal stenosis	X

	Ileal stenosis	X
	Jejunal stenosis	X
	Rectal stenosis	X
	Small intestine stenosis	X
	Rectal perforation	X
	Small intestine perforation	X
	Colonic perforation	X
	Duodenal perforation	X
	Ileal perforation	X
	Jejunal perforation	X
	Enterovesical fistula	X
	Renal and urinary disorders ¹	X
	Bladder perforation	X

¹ Specific to radiation / surgery treatment area

² Specific to ipsilateral extremity / region

ACUTE TOXICITIES – Lower Distal Extremity			
CTCAE System/Organ/Class (SOC)	Adverse Event / Symptoms	Baseline	During RT & Preoperative Assessment

General disorders and administration site conditions	Fatigue	X	X
Skin and subcutaneous tissue disorders	Dermatitis Radiation	X	X
	Hyperpigmentation	X	X
Neoplasm benign, malignant and unspecified	Tumor pain	X	X

¹ Per study definition

LATE TOXICITIES – Lower Distal Extremity		
CTCAE System/Organ/Class (SOC)	Adverse Event / Symptoms	Post-Surgery & Follow Up

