Skin and subcutaneous tissue disorders	Hyperpigmentation ¹	X
Vascular	Lymphedema ²	X
General disorders and administration site conditions	Localized edema ¹	X
Musculoskeletal and connective tissue disorders	Fibrosis deep connective tissue ¹	X
	Joint range of motion decreased ²	X
	Osteonecrosis ¹	X

Neoplasm benign, malignant and unspecified	Tumor pain ¹	X
Injury, poisoning and procedural complications	Fracture ¹	X

¹ Specific to radiation / surgery treatment area

² Specific to ipsilateral extremity / region

ACUTE TOXICITIES – Superficial Trunk			
CTCAE System/Organ/Class (SOC)	Adverse Event / Symptoms	Baseline	During RT & Preoperative Assessment
General disorders and administration site conditions	Fatigue	X	X
Skin and subcutaneous tissue disorders	Dermatitis Radiation	X	X
	Hyperpigmentation	X	X
Gastrointestinal disorders	Diarrhea	X	X
	Nausea	X	X
	Vomiting	X	X
Renal and urinary disorders	Dysuria	X	X
Neoplasm benign, malignant and unspecified	Tumor pain	X	X

LATE TOXICITIES		
CTCAE System/Organ/Class (SOC)	Adverse Event / Symptoms	Post-Surgery & Follow Up
Skin and subcutaneous tissue disorders	Hyperpigmentation ¹	X
General disorders and administration site conditions	Localized edema ¹	X
	Lymphedema	X
Musculoskeletal and connective tissue disorders	Fibrosis deep connective tissue ¹	X
	Joint range of motion decreased ²	X
	Osteonecrosis ¹	X
Neoplasm benign, malignant and unspecified	Tumor pain ¹	X
Injury, poisoning and procedural complications	Fracture ¹	X
Gastrointestinal Disorders ¹	Anal fistula	X
	Colonic fistula	X
	Duodenal fistula	X
	Esophageal fistula	X
	Gastric fistula	X
	Ileal fistula	X
	Jejunal fistula	X

	Rectal fistula	X
	Anal ulcer	X
	Colonic ulcer	X
	Duodenal ulcer	X
	Gastric ulcer	X
	Ileal ulcer	X
	Jejunal ulcer	X
	Rectal ulcer	X
	Small intestine ulcer	X
	Anal stenosis	X
	Colonic stenosis	X
	Duodenal stenosis	X
	Gastric stenosis	X
	Ileal stenosis	X
	Jejunal stenosis	X
	Rectal stenosis	X
	Small intestine stenosis	X
	Rectal perforation	X
	Small intestine perforation	X
	Colonic perforation	X
	Duodenal perforation	X
	Gastric perforation	X
	Ileal perforation	X

	Jejunal perforation	X
	Enterovesical fistula	X
Renal and urinary disorders ¹	Urinary fistula	X
	Bladder perforation	X
Respiratory, thoracic and mediastinal disorders	Pneumonitis ¹	X

¹ Specific to radiation / surgery treatment area

² Specific to ipsilateral extremity / region

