10.5 Submit via appropriate *reporting mechanisms* the following AEs experienced by a patient through the course of Radiation Therapy and not specified in Section 10.4:

10.5.1 Grade 3, 4, and 5 AEs regardless of attribution to the study treatment or procedure.

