16.3.2 Secondary Outcome Analysis

16.3.2.1 Local failure is defined any radiographic or pathologic evidence of recurrent disease inside the CTV and/ or to within 3 cm from the edge of the CTV. In the absence of censored patients prior to 5 years, local failure rate at 5 years (LFR5) will be equal to the binomial proportion. LFR5 will be evaluated by the number of patients free of local failure/recurrence at 5 year divided by the total number of evaluable patients. Exact binomial 95%

confidence interval for the point estimate will be provided. In the case of censoring prior to 5 years, LFR5 will be estimated using the Kaplan-Meier method.

- 16.3.2.2 Disease-Free Survival is defined as the time from registration date to the earliest date of documentation of either, local recurrence, regional recurrence, distant recurrence, or death due to any cause, censoring patients who are alive and local recurrence free at the date of last known clinical assessment. The distribution of disease-free survival will be estimated using method of Kaplan-Meier.
- 16.3.2.3 Overall Survival is defined as the time from registration date to death due to any cause, censoring patients alive at the date of last contact. The distribution of overall survival will be estimated using method of Kaplan-Meier.
- 16.3.2.4 Late toxicity is defined as toxicity occurs any time between 3 months and 24 months after completion of hypofractionated preoperative radiation therapy. The rate of \geq grade 2 late toxicities will be estimated by the number of patients with a \geq grade 2 late toxicity divided by the total number of evaluable patients. Exact binomial 95% confidence intervals for the true rate of \geq grade 2 toxicity events will be calculated.
- 16.3.2.5 Pattern of relapse will be evaluated by number of patients with patterns of tumor recurrence such as local recurrence, marginal recurrence, regional recurrence, distant metastasis, and second primary tumor divided by the total number of evaluable patients. Exact binomial 95% confidence interval for the point estimate will be provided.
 - 16.3.2.5.1 Local tumor recurrence is defined as any tumor recurrence inside the CTV.
 - 16.3.2.5.2 Marginal tumor recurrence is defined as any tumor recurrence beyond the CTV to within a 3 cm distance from the edge of the CTV.
 - 16.3.2.5.3 Distant tumor recurrence is defined as any tumor that develops distantly from the primary site of sarcoma.

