- 16.3.2.5.4 Second primary tumor is defined as any different histology of sarcoma or any other type of malignancy inside or outside the radiation field.
- 16.3.2.6 Adverse Events: All eligible patients that have initiated treatment will be considered evaluable for assessing adverse event rate(s). The maximum grade for each type of adverse event will be recorded for each patient, and frequency tables will be reviewed to determine patterns. Additionally, the relationship of the adverse event(s) to the study treatment will be taken into consideration. Late toxicities (as defined in sections 16.3.2.4) will be summarized separately.
- 16.3.2.7 Quality of Life Measurements – PROMIS-10: Results from the ten-item PROMIS questionnaire will be used to evaluate physical health and mental health, separately. Changes in raw score from baseline to 24-months post-surgery will be assessed, in each of the physical and mental health domains. The Wilcoxon signed-rank test will be utilized to assess changes in raw PROMIS scores. Mean change, along with standard deviation will be reported.
- A scoring table to compare this patient population to global means may be utilized for various timepoints. However, because this scoring table is prepared for a fixed set of items, it can only be used when an examinee responds to all of the items in the set. This, along with all other analyses, including graphical representations and comparisons between other timepoints or subgroups of patients may be performed, but will be considered exploratory.
- 16.3.2.8 Quality of Life Measurements – TESS: Results from the Toronto Extremity Salvage Score (TESS) questionnaire will be used to evaluate functional outcomes. The TESS specifically measures performance of activities of daily living, and is separated into upper and lower extremity versions (29 and 30 questions, respectively).
- Patients will fill out the appropriate version, and point totals will be summed. Mean change from baseline to 24 months post-surgery, along with standard deviation will be reported by version. The Wilcoxon signed-rank test will be used to assess changes in TESS scores within questionnaires. All other analyses, including graphical representations, GEE model creation, and comparisons between different timepoints or subgroups of patients may be performed, but will be considered exploratory.

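### Adverse event rates share one pooled denominator although section 10.4 solicits some items only in certain tumor sites, so low-grade acute GI and urinary rates fall below the rate among patients asked

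*Combined protocol and SAP*

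**What the plan says.** Section 16.3.2.6 defines the population for adverse event rates without reference to tumor site or item: "All eligible patients that have initiated treatment will be considered evaluable for assessing adverse event rate(s". It then describes the output: "The maximum grade for each type of adverse event will be recorded for each patient, and frequency tables will be reviewed to determine patterns". Late toxicities are to be summarized separately. The one late rate that is specified, in 16.3.2.4, is a composite: patients with at least one "grade 2 late toxicity divided by the total number of evaluable patients".

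Section 10.4 has five solicited lists, one per anatomical site, and they differ. It also narrows collection once radiation has ended: "so the focus is on solicited toxicities and not any adverse event after radiation therapy is completed".

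Two other provisions can pick up events that are not on a patient's list. Section 10.2.2 has new unlisted events in or close to the irradiated area graded, with attribution by the study PI. Section 10.5.1 requires, through the course of radiation and for events not specified in 10.4, submission of "Grade 3, 4, and 5 AEs regardless of attribution to the study treatment or procedure".

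**The concern.** A frequency table built on one pooled population treats a patient who was not asked about an item as a patient without the event. For an item solicited at only two of five sites, the tabulated rate then mixes the event's frequency with the trial's site mix. A reader comparing this regimen with other series could take a low figure as good tolerability when part of it reflects who was asked. The study aims to evaluate safety as well as efficacy (section 1.0), so these tables will be read.

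**Working it through.** **Which items are solicited where (section 10.4).** The last late table has no site in its title; it follows the trunk acute table and is read here as trunk.

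| Items | Upper proximal | Upper distal | Lower proximal | Lower distal | Trunk |
|---|---|---|---|---|---|
| Acute diarrhea, nausea, vomiting, dysuria | no | no | yes | no | yes |
| Late bowel fistula, ulcer, stenosis, perforation; bladder perforation | no | no | yes | no | yes |
| Late pneumonitis, esophageal fistula | yes | no | no | no | yes |
| Late gastric items | no | no | no | no | yes |

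**Routes for an acute GI or urinary event at a site that does not solicit it.**

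- Grade 3-5 during radiation: 10.5.1. One ambiguity remains. Not specified in 10.4 could mean absent from that patient's list or absent from all lists. On the second reading, Grade 3 diarrhea in a distal-limb patient falls outside 10.5.1.
- Grade 1-2: only 10.2.2, and only if the event counts as in or near the irradiated area.

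**Size of the pooled denominator.** The plan's figure is 108 evaluable patients (16.2), and it reproduces: n = [(1.2816 × √(0.45 × 0.55) + 0.8416 × √(0.35 × 0.65)) / 0.10]² = 107.95, rounded up to 108, with power 80.01%. Allowing for 10% loss, 108 / 0.90 = 120. The figure serves here only as a plausible denominator; the ratio below does not depend on it.

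**Effect on an item rate.** Let s be the share of evaluable patients in soliciting sites, p the rate among them, and q the rate recorded at the other sites.

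Pooled rate = s × p + (1 − s) × q, so pooled / p = s + (1 − s) × q / p.

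If nothing is recorded elsewhere (q = 0), the ratio is s. The documents do not state s, and section 5.0 places no restriction on enrollment by site, so s is an assumption. With N = 108 and about a 10% rate among patients asked:

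| s | Patients asked | Events | Rate among asked | Pooled rate | Ratio |
|---|---|---|---|---|---|
| 25% | 27 | 3 | 11.1% | 3/108 = 2.8% | 0.25 |
| 50% | 54 | 5 | 9.3% | 5/108 = 4.6% | 0.50 |
| 75% | 81 | 8 | 9.9% | 8/108 = 7.4% | 0.75 |
| 90% | 97 | 10 | 10.3% | 10/108 = 9.3% | 0.90 |

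Partial capture elsewhere softens this. With s = 50% and q half of p, the ratio is 0.50 + 0.50 × 0.50 = 0.75.

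**Other outputs.** The primary endpoint is wound complication, assessed at every site. The composite late rate counts any qualifying event, and every site has a late list. The stopping rule in 16.4.2 counts any Grade 3+ event at least possibly related to radiation, and 10.5.1 reaches Grade 3-5 events during radiation at every site, subject to the ambiguity above.

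**The case against.** The strongest reply has four parts.

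1. Patients at other sites are not simply unassessed. Section 10.2.2 carries no grade or time limit for unlisted events in or near the field, and 10.5 covers Grade 3-5 events during radiation. This stands: a reader might infer that such patients were never assessed, and the documents do not support that. They do leave Grade 1-2 diarrhea, nausea, vomiting or dysuria without a clear route when the field is remote from the organ.
2. The late GI, urinary and pneumonitis items carry a footnote limiting them to the radiation or surgery area. A distal-limb patient has essentially no bowel, bladder or lung there (an inference from anatomy), so is close to a structural zero and not a missing value. This stands: it would be wrong to call a whole-trial pneumonitis or fistula rate biased. It answers a different question from the rate among patients at risk.
3. The plan names a population and frequency tables; it does not spell out division of each item by that total, and it specifies no confidence interval for single events. This also stands. Division by the evaluable set is the natural reading of a rate, but a charge that planned per-item intervals are too narrow has no basis in the text.
4. Section 16.3 plans an exploratory comparison of proximal lower limb with the rest. The first group was asked all four acute items, so its rates are undiluted. The rest still mixes trunk, which was asked, with three sites that were not. This is only partial mitigation.

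**Conclusion.** The point holds for low-grade acute diarrhea, nausea, vomiting and dysuria. Under 16.3.2.6 as written, a pooled rate for these items is lower than the rate among patients asked, by a factor equal to the share of patients in the lower proximal and trunk sites. That assumes no events are recorded elsewhere; any capture through 10.2.2 or 10.5 moves the factor toward 1. The true factor cannot be computed from the documents: 0.50 and 0.75 are illustrations for shares of 50% and 75%.

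For the late fistula, ulcer, stenosis, perforation and pneumonitis items, the finding is one of labelling: the whole-trial rate and the rate among patients at risk are both valid, and the plan does not say which is meant. A reader might infer that the late-toxicity result or the safety stopping rule is compromised. The documents do not support that, because both count any qualifying event across all sites. The primary analysis is untouched. This is a modest, inexpensive correction to the safety tables.

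**What to change.** Add to 16.3.2.6, and apply to any per-item late-toxicity table:

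- An item that 10.4 solicits only at certain sites is reported over eligible patients at those sites who started treatment, with that n shown on the row.
- Events of the same type captured at other sites through 10.2.2 or 10.5 are listed separately as unsolicited, so that none is lost and none lacks a denominator.
- Any rate over all eligible treated patients is labelled as a whole-trial rate. Items solicited at every site keep the common denominator.

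It would also help to state in 10.5 whether events not specified in 10.4 means not listed for that patient's site.

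The cost is a few sentences and a row-specific n. Anatomic location is already recorded in the same five categories (12.5), so no new data, visits or patients are needed. The small downside is that rates for these items will look less favourable and be less precise. For example, if an exact 95% limit were computed for an item with no events, the upper bound would be 6.6% on 54 patients against 3.4% on 108.

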4.0 Test Schedule

	Pre-treatment/ Baseline ≤30 days prior to registration	Hypo-fractionated RT 42.75 Gy in 15 fractions	Post-RT Assessment (+/- 5 days)	Pre- Operative Assessment Within 2 weeks of surgery⁹	Post- Operative Assessment 4-8 weeks Post-Surgery^{6,9}	Years 1 & 2 Post-Surgery Assessment Every 6 Months Post-Surgery^{7,8,9} (+/- 8 weeks)	Years 3-5 Post-Surgery Assessment Annually Post- Surgery^{7,8,9} (+/- 8 weeks)
History, physical exam ⁷ , ECOG status	X		X	X		X	X
Pathology review ¹	X				X		
Primary site MRI ² , ⁵	X			X		X	X
PET/CT or CT Chest ⁵ ,	X			X		X	X
Pregnancy test ³	X						
AE Acute Assessment (See section 10.0)	X		X	X			
Hypofractionated RT		X					
CTCAE v5.0 Solicited Late Toxicity Assessment (See section 10.0)	X				X	X	X
Wound Complication Assessment (Appendix VI/Section 11.0)					X	X	
Regional Alopecia Assessment (Appendix V)	X		X	X			
Joint Stiffness Assessment (Appendix IV)	X		X	X		X	X
PROMISE-10 ^a	X			X		X ⁴	
TESS ^b	X			X		X ⁴	

1. Pathology review includes histopathologic diagnosis of soft tissue sarcoma and grade, where applicable.
2. CT is acceptable if MRI is not advisable.
3. For women of childbearing potential only. Must be done ≤7 days prior to beginning radiation treatment. Tubal ligation and IUD in place are exceptions.
4. Obtained at 12, 18, and 24 months.
5. Within 60 days of enrollment
6. Follow Up timepoints may be evaluated outside the anticipated window as deemed appropriate by Stand of Care Radiation Oncology and Orthopedic Surgery follow up schedule
 - a. Patient-Reported Outcomes Measurement Information System
 - b. Toronto Extremity Salvage Score
7. Assessments may be completed by NP/PA in person or by virtual and/or phone visit if patient is unable to return to study site.
8. Per physician discretion
9. If patient develops any type of disease progression or is unwilling to return to the institution, patients will move to yearly survival follow up. No additional assessments will need to be done.

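### The planned 24-month PROMIS-10 and TESS changes rest on patients with both scores, so they are likely too favourable as a description of all treated patients

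*Combined protocol and SAP*

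**What the plan says.** **Collection.** The Test Schedule (section 4.0) asks for PROMIS-10 and TESS at baseline, before surgery, and in the Years 1 and 2 column, where footnote 4 says: "Obtained at 12, 18, and 24 months". Section 7.4 expects every patient to complete both questionnaires. Objective 2.2.6 is to describe patient-reported outcomes with the regimen, and it does not limit this to progression-free patients.

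**Exit from collection.** Footnote 9, attached to that same column, reads: "If patient develops any type of disease progression or is unwilling to return to the institution, patients will move to yearly survival follow up". It adds: "No additional assessments will need to be done". Footnote 7 allows virtual or telephone assessment for patients who are unable to return.

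**Analysis.** For PROMIS-10 (16.3.2.7): "Changes in raw score from baseline to 24-months post-surgery will be assessed", and "The Wilcoxon signed-rank test will be utilized to assess changes in raw PROMIS scores". For TESS (16.3.2.8): "Mean change from baseline to 24 months post-surgery, along with standard deviation will be reported by version", and "The Wilcoxon signed-rank test will be used to assess changes in TESS scores within questionnaires". Other time points for both instruments, and a GEE model for TESS, are optional and exploratory. Neither section defines who is analysed or what happens when the 24-month score is missing. The adjacent adverse-event item (16.3.2.6) does say who is evaluable.

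**The concern.** A signed-rank test and a mean change both need two scores from the same patient. Footnote 9 makes a missing 24-month score a planned consequence of progression, which is itself a poor outcome, or of refusal to return. The patients who remain are therefore a selected group.

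The stake is how objective 2.2.6 will be read. With no stated population, a 24-month mean change will be taken as the experience of everyone treated, although it comes from those still in the assessment schedule. The trial has one arm, so no comparator shares the same attrition and offsets it.

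**Working it through.** **1. The plan's own figures.** The documents give no sample size, power or expected completion for the questionnaires. The only sample-size figure is for wound complications (16.2), and it reproduces:

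- n = [(z0.90 × √(0.45 × 0.55) + z0.80 × √(0.35 × 0.65)) / 0.10]² = 107.95, so 108.
- Power at 108 is 80.01%, and 108 / (1 − 0.10) = 120.

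This point does not affect those figures. The 10% loss in 16.2.2 refers to the 120-day endpoint and does not cover progression up to 24 months.

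**2. Bias of the observed-pair mean.** Let m be the share without a 24-month score, S the mean change in stayers and L the mean change in leavers. The mean over all patients is (1 − m)S + mL, while the observed-pair mean is S. The bias is S − [(1 − m)S + mL] = m(S − L).

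Both m and S − L are assumptions. The 108 is borrowed from the primary endpoint only to show scale; TESS is split by version, so its counts would be smaller.

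| Missing at 24 months | Pairs left of 108 | Gap 0.5 SD | Gap 1.0 SD |
|---|---|---|---|
| 20% | 86 | 0.20 × 0.5 = 0.10 | 0.20 × 1.0 = 0.20 |
| 30% | 76 | 0.30 × 0.5 = 0.15 | 0.30 × 1.0 = 0.30 |
| 40% | 65 | 0.40 × 0.5 = 0.20 | 0.40 × 1.0 = 0.40 |

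The results are in SD units because the documents give no SD or meaningful difference for either instrument.

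**3. Would using the 12- and 18-month scores remove the bias?** This was simulated with n = 108, visits at 0, 12, 18 and 24 months, an assumed between-visit correlation of 0.6, and exit at a uniform time. The pre-operative score was not included. A likelihood estimate using all visits was compared with the observed pairs.

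- *Decline is gradual and visible before exit:* with 30% missing and a gap of 1.0 SD, the bias falls from 0.30 to 0.25 SD. Across the scenarios the reduction is about 15% to 18%.
- *Decline starts at progression, when assessments stop:* 0.30 SD stays at 0.30 SD. No score records the decline, so no model can recover it.

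**4. Other dropout patterns.** These used 20% or 40% missing and a true mean change of zero.

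- *Dropout depends only on the previous observed score:* the observed pairs are off by −0.02 to −0.06 SD, slightly the unfavourable way. The all-visits estimate is within about 0.005 SD of the truth.
- *Dropout depends on the current, unseen score level:* the pairs are off by +0.01 to +0.05 SD and the all-visits estimate by +0.03 to +0.13 SD.

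The direction and size therefore depend on why patients leave, and the mixed model is not better under every pattern.

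**The case against.** The strongest reply is that this is a descriptive secondary objective in a single-arm trial. No decision rule uses the questionnaires, and longitudinal work is already foreseen: other time points for both instruments and a GEE model for TESS. Function among progression-free patients can also be a legitimate target. Footnote 9 lifts a requirement and does not forbid further questionnaires, and footnote 7 keeps patients who are unable, as opposed to unwilling, to return.

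Much of this stands, and it limits the point. It does not remove it. The longitudinal analyses are optional, GEE is named for TESS only, and neither can recover scores that were never collected. If progression-free patients are the target, the plan does not say so, while section 7.4 and objective 2.2.6 point to all patients.

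A reader might infer three stronger things that the documents do not support:

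- *That the plan restricts the analysis to disease-free patients who come back.* No sentence says this. The restriction follows from footnote 9, the paired test and the absence of a missing-data rule.
- *That a favourable bias of known size is established.* The direction assumes that patients who progress or leave fare worse, and the size cannot be computed from the documents.
- *That ignoring the 12- and 18-month scores causes the problem.* The main cause is that collection stops under footnote 9.

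**Conclusion.** The point holds as a likely bias of unknown size. The prespecified 24-month changes describe patients with both scores, and they are likely too favourable if read as describing all treated patients. The illustrative range is 0.10 to 0.40 SD. It rests on two assumptions that the documents neither give nor exclude: 20% to 40% missing at 24 months, and leavers' change 0.5 to 1.0 SD worse. Progression makes a worse course in leavers the natural expectation. If dropout instead followed only earlier scores, the bias would be small and slightly the other way.

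The primary endpoint and sample size are untouched. This is a worthwhile correction to a secondary analysis and does not threaten the trial's main conclusion.

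**What to change.** 1. **Name the target.** State in 16.3.2.7 and 16.3.2.8 whether the 24-month change refers to all treated patients or to those alive and progression-free, and how deaths are handled.
2. **Change the main analysis.** Use a repeated-measures mixed model with all scheduled scores (baseline, pre-operative, 12, 18 and 24 months), and keep the paired Wilcoxon test as supportive. The model uses partial records and is valid when dropout depends on observed scores.
3. **Add a missing-not-at-random sensitivity analysis**, for example a delta adjustment for patients who left at progression. The model alone does not deal with a decline that begins when collection stops.
4. **Report by visit** the number contributing and the reasons for missing scores.
5. **If the target is all treated patients, consider amending footnote 9** so that remote questionnaires continue after progression. The TESS form in Appendix III already lists mail and telephone completion. However, it covers TESS only, carries another study's label, and notes that the measurement properties of mailed use were not formally tested.

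**Cost.** Items 1 to 4 need SAP wording, one standard model and slightly more analysis on scores already scheduled, plus recording of reasons for missing scores. The main model brings a missing-at-random assumption. Item 5 is a protocol amendment with new data collection, and the sponsor may reasonably debate it.
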